# Table 1.Predicted Exposures and Margins Relative to Toxicokinetics Limits at
Planned PF-06252616 Doses

IV Dose (mg/kg)	Predicted C max (µg/mL)	Fold Difference with C max Cynomologus Monkey NOAEL	Predicted C av (µg/mL)	Fold Difference with C av Cynomolgus Monkey NOAEL
5	156	17.2	65	28.7
20	598	4.5	265	7.1
40	1200	2.2	550	3.4

Toxicology limit set by the NOAEL of 50 mg/kg in 26 week non-human primate juvenile study ( $C_{max} = 2690 \mu g/mL$ ,  $C_{av} = 1870 \mu g/mL$ ).

The predicted human AUC672 was converted to  $C_{av}$  as follows: AUC672/672 =  $C_{av}$ .

 $C_{max}$  = maximum concentration at steady-state;  $C_{av}$  = average concentration at steady state.

#### 1.11. Study Design Rationale

This study is a Phase 1b/2, open-label multiple ascending dose escalation study to evaluate the safety, tolerability, efficacy, PK and PD of PF-06252616 in ambulatory adults with LGMD2I. The study design is intended to determine the optimal safe and pharmacologically active dose of PF-06252616 in LGMD2I while providing an opportunity for all subjects to receive active

drug for a rare and disabling disorder. The study will be conducted in four periods: Lead-In, Treatment, Follow-up, and Extension periods. The Lead-In and Follow-up periods will each be approximately 16 weeks to allow an assessment of the change of various outcome measures of this period of time and comparison of change in function before, during and after treatment. The Treatment period will be 32 weeks. This time of active treatment was chosen to maximize the possibility of observing trends in efficacy. After the Follow-up period, the subject will be given the option to continue treatment in the Extension period.

This study is primarily a safety and tolerability study of PF-06252616 in LGMD2I adults. The rationale for dose selection and escalation has been described above. A limited number of patients (4) will be enrolled in cohort 1 and will receive an initial dose of 5mg/kg PF-06252616 IV every 4 weeks. Following 16 weeks of treatment and a safety review, if no stopping rules have been met, 8 subjects will be enrolled in cohort 2 and receive 20mg/kg of PF-06252616. Subjects in cohort 2 will received 16 weeks of treatment and then a safety review will be performed. If no stopping rules have been met, cohort 1 will escalate to receive 40 mg/kg. This will occur after they have already received 5 mg/kg of PF-06252616 for 32 weeks. At the same time, cohort 3 will be enrolled and begin dosing at 40 mg/kg. For cohort 1, subject will receive 32 weeks of treatment with 5 mg/kg followed by an additionl 32 weeks of treatment with 40 mg/kg PF-06252616. The rationale for this design is that it provides a dose escalation to determine safety of each dose and allows each cohort to potentially receive a meaningful dose. Thirty-two weeks of treatment maximizes the opportunity to determine if there is a treatment effect at any given dose level. Finally, the design will provide long-term, 64 week dosing data on a limited number of subjects (4). All subjects, who completed the Follow-up period, will have the option to continue treatment in the extension period at 40mg/kg for up to 28 weeks in Cohort 1, up to 40 weeks in Cohort 2, and up to 24 weeks in Cohort 3

Exploratory outcome measures of efficacy will also be obtained. There has been only one published drug intervention trial to date which has included LGMD2I subjects . This was a trial of myostatin neutralizing antibody MYO-029 which was trialed in subjects with various different adult muscular dystrophies. Various assessments of efficacy were obtained in this trial including manual muscle testing (MMT), quantitative muscle testing (QMT), timed function tests (TFTs), pulmonary function tests (PFTs), MRI, DXA and subject-reported outcomes. These assessments of efficacy were found to be feasible in the LGMD2I population. However, no efficacy was found in the combined LGMD group to provide information on optimal outcome measures for LGMD. There is one published natural history study on adult LGMD21. In this study various functional outcome measures were studied in 32 individuals over 12 months. QMT, timed up and go (TUG), 4 stair-climb (4SC), 4 stairdescend (4SD), 10 meter run (10MR), 6 minute walk test (6MWT) and forced vital capacity (FVC) were assessed. Of these functional measures, only FVC had a statistically significant decline in 12 months. The study also evaluated fat fraction by quantitative Dixon MRI and found increased fatty infiltration in 9 of 14 muscles within 12 months. Qualitative assessment of T1 weighted MRI was insensitive to change within this time frame. FVC and quantitative Dixon MRI therefore are high priorty outcome measures of this trial. However, considering the possibility that PF-06252616 will improve function rather than stabilize function, other outcome measures will be included as described above.

## 1.12. Anticipated Risks and Safety Monitoring

Complete information for this compound may be found in the Single Reference Safety Document, which for this study is the Investigator's Brochure.

Anticipated risks are based on clinical and toxicology data.

A total of 53 healthy adult subjects have received PF-06252616 in a phase 1 study. Forty-two received single IV or SC doses and 11 received a repeat dose (3 doses of 10 mg/kg PF-06252616 IV over a 4 week period). There are no safety findings of concern from this study. In 1 month toxicology studies performed with PF-06252616 in rat and monkey, no adverse findings were reported. Consistent with the pharmacological response anticipated from this anti-myostatin monoclonal antibody, effects on skeletal muscle were noted. In the 26-week repeat dose toxicity studies in juvenile rats and monkeys, adverse and/or clinically relevant findings were noted and provide the basis of the warnings and precautions below.

## 1.12.1. Hepatic Injury

Accumulation of iron in the liver resulting in fibrosis and single cell necrosis of the liver is considered a potential side-effect of treatment with PF-06252616. In the intended indication of LGMD2I, transaminase elevation related to muscle pathology is common. Alternative biomarkers of liver injury that are not affected by muscle pathology include GGT and GLDH which will be monitored in this trial. The prevention of hepatic iron accumulation is the best strategy for avoidance of liver injury in this disease. Approaches developed in the treatment and prevention of hepatic damage in haemochromatosis and iron overload syndromes provide a basis for monitoring using % Transferrin saturation (serum iron/total iron binding capacity x 100) and MRI measurement of hepatic iron.

Abnormal values for serum ALT or AST concurrent with abnormal elevations in total bilirubin that meet the criteria for Hy's law and in the absence of other causes of liver injury are considered potential cases of drug-induced liver injury (potential Hy's law cases) and should always be considered important medical events. Subjects meeting these criteria will follow the steps for confirmation required in Section 8.6.2. The utility and necessity of continued monitoring of liver iron by MRI will be formally reviewed prior to dose escalation.

## 1.12.2. Gastric Erosion and Haemorrhage

An increase in gastric erosion and haemorrhage was seen at necropsy observed in male rats administered 471.5 mg/kg/week for 26 weeks. Study subjects will be asked specifically to report symptoms that may be associated with such pathology. Monitoring of haemoglobin, haematocrit and fecal occult bloods will be performed.

## 1.12.3. Bone Metabolism

In the 26 week rat study, bone biomarker changes were identified suggestive of a decrease in bone turnover. Bone mineral density (BMD) as measured by peripheral quantitative computed tomography however was generally increased at the end of the study. The biomarker changes were reversible. In the monkey studies BMD and bone strength was increased. A positive effect on BMD would clearly be considered a positive PD effect. Spine and hip DXA will be used to monitor for changes in bone mineral density.

## 1.12.4. Cardiac

Based on recent literature on the biology of GDF-8 and GDF-11 in modulation of cardiomyocyte and cardiac function and the potential for cardiac dysfunction in the target population of LGMD2I subjects, it is appropriate to focus on the potential for an interaction. In monkey toxicity studies up to 26 weeks, no abnormality of cardiac function or histology was observed. In rats dosed with  $\geq$ 150 mg/kg/week for 26 weeks, a reduction in heart weight was noted, but there were no microscopic findings. In light of the hypothetical risk of an effect of PF-06252616 on cardiac muscle development or function, monitoring with 12-lead ECG for rhythm or morphological change by echocardiography to evaluate left ventricular ejection fraction (LVEF) and left ventricular end systolic volume (LVESV) and cardiac Troponin I for cardiac muscle tissue injury will be performed. Additional cardiac parameters (eg, cardiac strain) may be collected by echocardiogram for exploratory analyses. Abnormal values for each of these measures have been reported in LGMD2I . In light of the variability of findings in disease, no pre-specified stopping rules have been defined.

## 1.12.5. Special considerations in females

In the 26-week female juvenile rat toxicity study, adverse hepatic changes were seen at all doses, and a NOAEL was not identified. Female cynomolgus monkeys were not different from males in their sensitivity to iron accumulation or hepatocellular injury. It is possible therefore that in human studies, females may have a higher sensitivity to liver injury and appropriate care is taken to monitor using GLDH and iron parameters.

Reproductive and developmental toxicity studies with PF-06252616 have not been conducted. In the absence of evidence to the contrary, it must be assumed that administration of PF-06252616 would pose a risk to the fetus in early pregnancy. Adult female patients who are of child bearing potential may be enrolled into clinical studies with PF-06252616 if they are using at least one highly effective means of contraception as outlined in the Section on Contraception. These methods must be in place at the start of screening continued until the final study visit.

In a 26-week juvenile cynomolgus monkey study, there was no evidence of menses and marked arrested development of sexual organs was noted in female cynomolgus monkeys dosed at 284 mg/kg/week. These changes were partially to fully reversible. Despite >3x margin from the NOAEL exposure at the dose of 40 mg/kg/4 weeks, it is appropriate to monitor adult female patients reproductive health.

## 1.12.6. Radiation

Possible risks related to subject's undergoing evaluation with DXA include the risk of radiation exposure. The average effective dose of radiation received for a single DXA scan may vary due to the instrument and the subject's body. Subject may require a skull X-ray prior to MRI if there is a question of intraocular metal. This skull X-ray also carries the risks associated with radiation exposure. The maximum amount of radiation that a subject could receive is from 5 whole body DXA scans (in cohort 1), 3 DXA scans of the hips, 3 DXA scans of the spine and 1 skull X-ray. The expected total radiation dose for this maximum exposure is not expected to exceed 30 mrem. This is less than 1 year of natural background radiation which is approximately 300 mrem per year .

## 1.12.7. Needle Muscle Biopsy

Needle muscle biopsy is used to obtain small amounts of tissue (milligrams) for molecular studies in a clinic setting without the requirement of recovery time. Needle muscle biopsies have been used previously in clinical trials of muscular dystrophy for this purpose where histology is not needed . There is a risk of reaction to local anesthesia (1% lidocaine with 1:100,000 epinephrine). There is also a risk of bleeding, bruising, hematoma formation, infection and peripheral nerve damage. The combined risk of any of these adverse events occurring from needle muscle biopsy is estimated to be less than 1%.

## 1.12.8. Other possible risks

Possible risks related to the administration of the study drug and/or as a consequence to phlebotomy may include hematoma or bruising.

## 1.12.9. Other Safety Monitoring

Additional safety monitoring will include the parameters of adverse events (AEs), physical examination, vital signs, and clinical laboratory parameters (comprehensive metabolic panel [sodium, postassium, chloride, carbon dioxide, blood urea nitrogen, creatinine, calcium, glucose, total protein, albumin, total bilirubin, AST, ALT, alkaline phosphatase], gamma-glutamyl transferase [GGT], glutamate dehydrogenase [GLD], prothrombin time [PT], activated partial thromboplastin time [aPTT], creatine kinase, amylase, cardiac troponin I and urinalysis) and Columbia Suicide Severity Rating Scale (C-SSRS). Laboratory monitoring will also be performed to detect ADA and NAb.

## 1.13. Summary of Risk Benefit

This is a therapeutic study being conducted in adult subjects with LGMD2I. There is no accepted pharmacological treatment for this disorder. There has been only one other therapeutic trial to date in this rare disease which did not demonstrate efficacy. PF-06252616 may demonstrate pharmadynamic activity in subjects.

In view of the initial clinical evidence of safety and the monitorable nature of key nonclinical toxicological findings, data support an acceptable risk profile for PF-06252616 in the current study and support a favorable benefit risk profile in the indication of LGMD2I. Authorities will be kept informed of any additional data (eg, results from clinical studies) which may affect the assessment of the risk/benefit ratio for PF-06252616.

## 2. STUDY OBJECTIVES AND ENDPOINTS

## 2.1. Objectives

## 2.1.1. Primary

• To determine the safety and tolerability of multiple ascending repeat IV doses of PF-06252616 in ambulatory participants with LGMD2I.

## 2.1.2. Secondary

• To assess the PK exposures of PF-06252616 in LGMD2I.

- To evaluate the PD activity of PF-06252616 based on GDF-8 (myostatin) modulation in blood and in tibialis muscle.
- To characterize the functional effects of PF-06252616 on muscle strength and functional assessments compared to baseline.
- To characterize the effects of PF-06252616 on respiratory function compared to baseline.
- To characterize the effects of PF-06252616 on patient reported outcome measures.
- To evaluate the immunogenicity of PF-06252616.

### 2.1.3. Exploratory

- To evaluate functional outcome measures in LGMD2I.
- To evaluate the PD activity of PF-06252616 based on the percent change of muscle volume as measured on MRI compared to baseline as indicated by the whole body MRI evaluation and/or lean body mass DXA results.

## 2.2. Endpoints

## 2.2.1. Primary Safety

- Incidence of dose limiting or intolerability treatment related AEs by day 337 or 561.
- Incidence, severity and causal relationship of treatment emergent AEs (TEAEs) and withdrawals due to TEAEs by day 337 or 561.
- Incidence and magnitude of abnormal laboratory findings (clinical laboratory tests [hematology, chemistry], GGT, GLDH, PT, aPTT, creatine kinase, amylase, serum ferritin, serum iron, % transferrin saturation, Total Iron Binding Capacity (TIBC), LH, FSH, estrogen, cardiac troponin I, fecal occult blood and urinalysis) by day 337 or 561.
- Abnormal and clinically relevant changes in liver MRI and physical examinations, weight, vital signs, ECG, echocardiogram measured LVEF, DXA (bone mineral density), menstruation cycle (as monitored by diary), and C-SSRS (See Appendix 1 and Appendix 2) parameters by day 337 or 561.

## 2.2.2. Seconday Endpoints

#### 2.2.2.1. Pharmacokinetic

- All subjects receiving active drug: serum PF-06252616 Cmax and Ctrough for all visits with PK collections and at steady-state.
- Total serum GDF-8 concentrations for all visits with GDF-8 collections

## 2.2.2.2. Strength and Function

- Mean change from baseline on function tests including PUL, Timed up-and-go (TUG), 10-meter walk/run (10MR), 2-meter walk test (2MWT), and 4 stair climb (4SC)
- Mean change from baseline on pulmonary function tests incuding forced vital capacity (FVC), FEV1(forced expiratory volume in 1 second), maximal inspiratory pressure (MIP) and maximal expiratory pressure (MEP)
- Mean change from baseline on muscle strength by manual muscle test (MMT) and Hand-Held dynamometry

### 2.2.2.3. Patient Reported Outcomes

• Mean change from baseline on Patient reported outcomes (InQoL, SF-36)(See Appendix 3 and Appendix 4)

### 2.2.2.4. Immunogenicity

Incidence of ADA and NAb development.

### 2.2.3. Exploratory Endpoint

#### 2.2.3.1. Pharmacologic

- Mean percent change from baseline in lean body mass by DXA
- Mean percent change from baseline in muscle quality (fat infiltration) as measured by quantitative Dixon
- Mean change from baseline in muscle quality as measured by T1/STIR

#### **2.2.3.2.** Function

• Evaluate the utility and changes from baseline of Functional Workspace as an outcome measure for LGMD2I

#### 2.2.3.3. Pharmacodynamic

• Mean percent change from baseline in muscle volume as measured on MRI as indicated by the whole body MRI evaluation and/or lean body mass DXA results.

## **3. STUDY DESIGN**

#### 3.1. Study Overview

This is a Phase 1b/2, open-label multiple ascending dose study to evaluate the safety, tolerability PK and PD of PF-06252616 administered to ambulatory participants diagnosed with LGM2I. Three IV infused dose levels administered every 28 days will be investigated in a dose escalating fashion.

PF-06252616 dose levels:

- 5 mg/kg.
- 20 mg/kg.
- 40 mg/kg.

Approximately 20 eligible subjects will be consecutively assigned to 1 of 3 cohorts for approximately 96 weeks (cohort 1) or 64 weeks (cohorts 2 and 3).

**Cohort 1 (n=4):** 

- Lead-in period (16 weeks)
- Treatment A: PF-06252616 5 mg/kg (32 weeks)
- Treatment B: PF-06252616 40 mg/kg (32 weeks)
- Follow-up period (16 weeks)
- Extension period: PF-06252616 40 mg/kg (28 weeks)

## Cohort 2 (n=8):

- Lead-in period (16 weeks)
- Treatment: PF-06252616 20 mg/kg (32 weeks)
- Follow-up period (16 weeks)
- Extension period: PF-06252616 40 mg/kg (40 weeks)

## Cohort 3 (n=8):

- Lead-in period (16 weeks)
- Treatment: PF-06252616 40 mg/kg (32 weeks)
- Follow-up period (16 weeks)
- Extension period: PF-06252616 40 mg/kg (24 weeks)

[figure not shown]
At each dose level, subjects will be followed for an initial approximate 16-week lead-in period to establish individual change in disease progression.

The study will begin with 4 subjects being enrolled into Cohort 1. Following the lead-in period, subjects in Cohort 1 will be dosed with 5 mg/kg for a total of 32 weeks (8 doses). Cohort 2 will begin dosing at the mid dose level (20 mg/kg) once safety has been confirmed with subjects in Cohort 1 who have been treated for 16 weeks. Cohort 1 and 3 will begin dosing at the highest dose level (40 mg/kg) once safety has been confirmed with subjects in Cohort 2 who have been treated for 16 weeks.

Each dose level will be evaluated for 32 weeks (8 doses each). Cohort 1 is the only cohort who will receive 2 dose levels (5 mg/kg and 40 mg/kg) and their total treatment time will be a minimum of 64 weeks. Subjects in Cohort 1 will only receive 8 doses of the 5 mg/kg dose and not proceed to the 40 mg/kg dose until safety review and approval by the SMC.

At the conclusion of the treatment period, subjects will be followed for an additional 16 weeks to monitor for safety, PK and duration of response.

All subjects completing the follow-up period will have the option to continue treatment with 40mg/kg dose in the Extension Period.

## 3.2. Duration of Subject Participation

Subject's participation will begin during screening (up to 2 weeks) followed by a lead-in period (16 weeks), treatment period (64 weeks for Cohort 1, 32 weeks for Cohorts 2 and 3), follow-up period (ending 16 weeks after the last study dose in the treatment period), and the extension period (up to 28 weeks for Cohort 1, up to 40 weeks for Cohort 2, and up to 24

weeks in Cohort 3). Periods of participation are estimates and are dependent on enrollment and safety review of concurrent dosing cohorts. Subjects will return to the site monthly for study drug administration as well as completion of safety and efficacy assessments.

In order to ensure consistency in assessment collection, visits that include functional assessments and imaging assessments (DXA and WB-MRI) will be collected over 2 consecutive days, within the study visit window. In the case where subjects are traveling from a distance, the site will offer nearby overnight accommodations.

### 3.3. Approximate Duration of Study

The study is estimated to complete in approximately 151 weeks allowing for 27 weeks of enrollment and up to124 weeks on the study.

The end of the study will be the last visit of the last subject for purposes informing the institutional review board/ethics committee (IRB/EC), and ceasing to send Council for International Organizations of Medical Sciences (CIOMS) reports.

#### 3.4. Planned Number of Subjects

A minimum of 20 subjects will participate. In order to ensure adequate enrollment, a sufficient number of subjects may be screened.

### 3.5. Safety Monitoring and Dose Escalation

Safety monitoring will be conducted by the Investigator, Pfizer Medical Monitor and an External Medical Monitor. This group will be referred to as the Safety Monitoring Committee (SMC). Safety monitoring by these individuals will include the following reviews:

- Dose escalation
- Quarterly safety and
- Ad hoc safety

At each review, a consideration will be made of the number of subjects who have severe AEs or serious AEs in the same organ system which are determined to be related to investigational product. The SMC may determine it is necessary to close or adjust a dose level within the study. The first dose escalation decision, whether or not to increase from 5 mg/kg in Cohort 1 to 20 mg/kg in Cohort 2 will occur after review of all safety data after the 4th subject of Cohort 1 has completed the planned 16 weeks (day 85) or 4 doses. The second dose escalation decision, whether or not to increase from 20 mg/kg in Cohort 2 to 40 mg/kg in Cohorts 1 and 3 will occur after the 4th subject in Cohort 2 had completed the planned 16 weeks (day 85) or 4 doses. A break in dosing of subjects in Cohort 1 between 5 mg/kg and 40 mg/kg may occur to ensure all safety data from Cohort 2 at 20 mg/kg has been evaluated by the SMC. Should a break be required in Cohort 1 between Day 197 and 225 ( $\pm$ 3 days) which is longer than the planned 28 days between dosing visits and outside the visit schedule, the window will not be applied. When the dosing resumes in Cohort 1 at the highest dose, the first day of dosing will be Visit 11 and the remaining dosing schedule will follow the Schedule of Activities, whereby dosing will occur every 28 days ( $\pm$  3 days).

## **3.5.1. Dose Escalation and Stopping Rules**

DECISION	CRITERIA				
Dose Escalation	SMC review of aggregate safety data from either:				
	• Cohort 1 (n=4) 16 weeks (day 85) or				
	• Cohort 2 (n=4) 16 weeks (day 85)				
	and agree that safety is met and				
	The estimate as determined by R2* value is within the normal range (R2* $\leq$ 139 Hz at 3.0 T ) $^{17,21,26}$				
No Esclation, Stop Dosing	SMC review of aggregate safety data from either:				
	• Cohort 1 (n=4) 16 weeks (day 85) or				
	• Cohort 2 (n=4) 16 weeks (day 85)				
	And agree that the current dose is not safe or				
	The liver iron content estimate as determined by R2* value is above the "mild overload" range for any subject within the cohort (R2* >369 Hz at 3.0 T) $^{17,21,26}$				

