j. Prep B1.5 (K2 EDTA plasma collection optimized for biomarker/proteomic/metabonomic analysis), Prep B2.5 (serum collection optimized for biomarker/ proteomics/metabonomic analysis), Prep R1 (PAXGene whole blood collection optimized for RNA analysis), and Prep 4 (Cell-free RNA) will be collected at: Cohort 1 at Visit 27, Cohort 2 at Visit 22, and Cohort 3 at Visit 18, or at Early Termination.

MRI of the liver is performed on Visit 27 for Cohort 1, Visit 22 for Cohort 2, and Visit 18 for Cohort 3, or at Early Termination.

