## Table 2. Criteria to Determine Dose Escalation or Stopping

If dosing is terminated at any dose level, subjects will continue to be followed for resolution of the safety finding or until a new baseline is established. Depending on the nature of the reason for stopping dosing, the SMC will consider if the enrolled subjects can be continued at a lower dose level.

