## 3.5.2. Safety Monitoring Committee (SMC)

The SMC will be composed of three members: The Investigator, Pfizer Medical Monitor and an External Medical Monitor. The External Medical Monitor will be a clinical trialist and an expert in the neuromuscular field. The External Medical Monitor will not be a member of the the Investigator's institutions (Johns Hopkins School of Medicine [JHSOM] and Kennedy Krieger Institute [KKI]) nor an employee of Pfizer. The SMC will be responsible for ongoing safety monitoring from the initiation of the study through the final study visit. Reviews will include aggregate safety, targeted medical events of special interest including liver toxicity, and serious AE data. The SMC may also complete ad hoc safety reviews. Ad hoc PK data may be provided to the SMC as requested.

Following the data review, the SMC will determine if the study should be continued with no changes, modified, or stopped (eg, due to safety). Decision to continue the study must be unanimous. Decision to stop the study can be made by any of the three members. In all other decisions, the External Medical Monitor will cast the deciding vote. The recommendations made by the SMC to modify the the study will be forwarded to JHSOM IRB for final decision. At any time the SMC may indicate that the limit of safety and/or tolerability has been reached and that any of the dose levels will be removed from the study.

The SMC will consider the following safety criteria during their safety review:

- The number of subjects who have severe AEs or serious AEs in the same organ system which are determined to be related to study medication.
- Other findings that indicate that dose escalation should be halted.

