#### **Prior to dosing, the following procedures will be completed:**

- Physical Examination, including Nose and Throat Mucosal Exam
- **Pregnancy Test**: A highly sensitive urine pregnancy test will be performed on all female subjects
- Diary Cards: For collection of first day of each menstrual cycle for WOCBP.
- Contraception Review: Confirmation of use of acceptable forms of contraception
- Weight
- Vital signs: Supine blood pressure, pulse rate, respiratory rate, and oral temperature.
- **12-lead ECG:** ECGs will be performed in triplicate
- Clinical laboratory tests:
  - Hematology with complete blood count and differential, comprehensive metabolic panel (sodium, potassium, chloride, carbon dioxide, blood urea nitrogen, creatinine, calcium, glucose, total protein, albumin, total bilirubin, AST, ALT, alkaline phosphatase) gamma-glutamyl transferase (GGT), prothrombin time (PT), activated partial thromboplastin time (aPTT), creatine kinase, amylase, cardiac troponin I. Urinalysis.
- Serum ferritin, serum iron, % transferrin saturation, TIBC: fasting blood collection
- Horomone Testing: LH, FSH, estrogen in WOCBP
- GLDH
- **Fecal occult blood**: Fecal sample is to be collected at home within 1 week prior to scheduled visit.
- C-SSRS

- Immunogenicity: Baseline
- PD sample collection: Predose
- PK sample collection: Predose
- **MRI-liver**: Liver MRI will be obtained for iron accumulation (visit 11 only)
- **MRI-muscle:** WB-MRI and dedicated thigh MRI will be performed for muscle quantity and quality
- **DXA Whole Body:** Whole body DXA will be performed for lean body mass.
- **DXA Spine and Hip:** Spine and hip DXA will be performed for BMD.
- **Functional assessments:** Must be conducted in the following order: Respiratory function (FVC, FEV1, MIP, MEP), 4SC, 2MWT, 10-meter walk/run, TUG, strength assessment (MMT, hand-held dynamometry) and PUL.
- Quality of Life assessments
  - InQol
  - SF-36

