#### 7.10. Triggered Requirements

Condition/ Criteria	Action
Moderate Iron overload/ If the liver iron content	The subject should be referred to a hepatologist for
estimate as determined by R2* value is above the "mild	further assessment
overload" range (R2* >369 Hz at 3.0 T	
Cardiomyopathy/ If the LVEF falls 10% of baseline on	The subject should be referred to a cardiologist for
the cardiac echocardiogram at any follow-up visit	further assessment.

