2.2.1. Dose Escalation and Stopping Rules

DECISION	CRITERIA
Dose Escalation	SMC review of aggregate safety data from either:
	• Cohort 1 (n=4) 16 weeks (day 85) or
	• Cohort 2 (n=4) 16 weeks (day 85)
	and agree that safety is met and
	The estimate as determined by R2* value is within the normal range (R2* \leq 139 Hz at 3.0 T) ^{1,2,3}
No Escalation, Stop	SMC review of aggregate safety data from either:
Dosing	• Cohort 1 (n=4) 16 weeks (day 85) or
	• Cohort 2 (n=4) 16 weeks (day 85)
	And agree that the current dose is not safe or
	The liver iron content estimate as determined by $R2^*$ value is above the "mild overload" range for any subject within the cohort ($R2^* > 369$ Hz at 3.0 T) ^{1,2,3}

Table 1. Criteria to Determine Dose Escalation or Stopping

If dosing is terminated at any dose level, subjects will continue to be followed for resolution of the safety finding or until a new baseline is established. Depending on the nature of the reason for stopping dosing, the SMC will consider if the enrolled subjects can be continued at a lower dose level.

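### At 40 mg/kg, including extension entry, the only clearly prespecified action on R2* above 369 Hz is a hepatology referral; the stop rule names only the 5 and 20 mg/kg reviews

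*Protocol*

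**What the plan says.** Protocol 3.5.1, Table 2, has two rows, one for escalating and one for stopping. Each begins with an SMC review of one of two data sets: four Cohort 1 subjects at Day 85 (5 mg/kg), or "Cohort 2 (n=4) 16 weeks (day 85") (20 mg/kg). Escalation requires R2* of 139 Hz or less at 3.0 T. The stop row is met if the committee judges the dose unsafe, or if any subject in the cohort exceeds 369 Hz. SAP 2.2.1 repeats the table; its stop row reads "And agree that the current dose is not safe", then an *or*, then the R2* clause. Neither version names Cohort 3, Cohort 1 Treatment B or the extension. The text under the table opens with "If dosing is terminated at any dose level" and describes what follows a termination.

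Protocol 7.10 takes the same value, above 369 Hz, and gives one action: "The subject should be referred to a hepatologist for" further assessment. It gives no dosing instruction.

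Protocol 3.5.2 adds a general power: "At any time the SMC may indicate that the limit of safety and/or tolerability has been reached". No R2* figure is attached to it.

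For the extension, Protocol 3.1 says: "All subjects completing the follow-up period will have the option to continue treatment with 40mg/kg dose in the Extension Period". Within the extension, the schedule footnote says: "MRI of the liver is performed on Visit 27 for Cohort 1, Visit 22 for Cohort 2, and Visit 18 for Cohort 3". Those visits are the final dosing visits; a subject who leaves early is scanned on leaving instead. For Cohort 1's switch to 40 mg/kg, section 6.3 lists before dosing: "Liver MRI will be obtained for iron accumulation (visit 11 only").

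**The concern.** A numerical liver-iron limit on dosing is written for the two lower doses. It is not clearly carried to the dose where exposure is highest. Read literally, one R2* value can stop dosing at 5 or 20 mg/kg and lead only to a referral at 40 mg/kg.

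The toxicology in section 1.7 makes this more than a drafting point. In the 26-week monkey study iron accumulated at every dose, including the 50 mg/kg NOAEL dose, so the margin at 40 mg/kg is measured against an exposure at which iron still built up. At the top dose the deposits did not reverse over 13 weeks of recovery. Section 1.12.1 treats preventing accumulation as the main protection against liver injury and notes that muscle disease often raises transaminases, which makes them a poor guide here.

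The issue is subject protection. R2* results are tabulated either way (Protocol 9.3.4, SAP 8.2.1.5), so no analysis is biased.

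**Working it through.** **1. Exposure margins (Protocol Table 1).** Margin = monkey NOAEL exposure / predicted human exposure, with NOAEL Cmax 2690 and Cav 1870 µg/mL.
- 5 mg/kg: 2690/156 = 17.2; 1870/65 = 28.8 (the protocol prints 28.7).
- 20 mg/kg: 2690/598 = 4.5; 1870/265 = 7.1.
- 40 mg/kg: 2690/1200 = 2.2; 1870/550 = 3.4.

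The protocol's figures reproduce apart from that last digit, and the margin is smallest at 40 mg/kg.

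**2. Subjects in the named reviews.** 4 (Cohort 1) + 4 (Cohort 2) = 8 of 20, none of them on 40 mg/kg at the time.

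**3. Planned doses (schedules of activities).**
- Main period: Cohort 1 4 × 16 = 64; Cohort 2 8 × 8 = 64; Cohort 3 8 × 8 = 64; total 192.
- Main period at 40 mg/kg: 4 × 8 + 8 × 8 = 96, or 50%.
- Extension, if everyone opts in: 4 × 7 + 8 × 10 + 8 × 6 = 28 + 80 + 48 = 156, all at 40 mg/kg.
- All 40 mg/kg: (96 + 156)/(192 + 156) = 252/348 = 72%.

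Table 3.2 gives Cohort 2 ten extension dosing visits, but the dosing schedule in section 5 lists nine days. With nine, the extension has 28 + 72 + 48 = 148 doses and the share is 244/340, still 72%.

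**4. Key scans that could drive a dosing decision at 40 mg/kg.** None has a clearly prespecified dosing action for R2* above 369 Hz.

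| Liver MRI | 40 mg/kg doses still to come |
|---|---|
| Cohort 1 Visit 11 (Day 225, predose) | 8 of 8 |
| Cohort 1 Visit 14 (Day 309); Cohort 3 Visit 6 (Day 85) | 8 − 3 = 5 if read before that visit's dose; 8 − 4 = 4 if after |
| Cohort 1 Visit 20 (Day 561) | up to 7 in the extension; 7 − 1 = 6 before the next scheduled liver MRI |
| Cohort 2 Visit 12 (Day 337) | up to 10; 10 − 1 = 9 before the next |
| Cohort 3 Visit 12 (Day 337) | up to 6; 6 − 1 = 5 before the next |

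The last three rows assume that the final-visit MRI precedes that visit's dose, as the order in section 6.12 suggests.

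**5. Time without a scheduled liver MRI across extension entry.** Cohort 1: (757 − 561)/7 = 28 weeks. Cohort 3: (505 − 337)/7 = 24 weeks. Cohort 2: the tenth dose falls on Day 365 + 9 × 28 = 617, so (617 − 337)/7 = 40 weeks. On the nine listed days the last is Day 589, which gives 36 weeks and 8 intervening doses.

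**6. The step to 40 mg/kg.** Section 3.5 describes the second escalation decision as covering Cohorts 1 and 3. Cohort 2's later rise from 20 to 40 mg/kg in the extension is not named, so Table 2's limit of 139 Hz is not expressly applied to it.

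**The case against.** The best counter-argument is textual. The R2* clause follows its own *or* and has its own unit, any subject in the cohort; the sentence below the table refers to any dose level. Read that way, it is a standing rule that already stops dosing at 40 mg/kg and also reaches Cohort 2 subjects 5 to 8. This reading is possible. But the row still names only two cohorts at Day 85, and the sentence below says what happens after termination without setting a trigger. On this reading Table 2 and section 7.10 give different actions for one value. They can be reconciled, since a subject can be referred and also held, but the protocol does not say so.

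The second argument is that discretionary protection is substantial. The SMC reviews safety quarterly and ad hoc, with liver toxicity as a targeted event. Continuing needs all three members to agree, and any one can stop the study. A referral would probably also make the finding a reportable AE under section 8.5. All of this stands, and 40 mg/kg is not unprotected. None of it supplies an R2* threshold for dosing.

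Third, MRI is not the only monitor. Iron indices, GGT and GLDH are drawn during the extension at Cohort 1 Visit 24, Cohort 2 Visits 16 and 19, and Cohort 3 Visit 15. The last pre-extension scan is also 28 days before the first extension dose, which leaves time to act. These points soften the gap; the 28 days also make an entry check easy to run.

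Finally, 72% is a count of doses. It says nothing about how often R2* would exceed 369 Hz, for which the documents give no rate.

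**Conclusion.** The concern holds. As written, the R2* stop criterion is tied to Day 85 reviews at 5 and 20 mg/kg. At 40 mg/kg, including extension entry, the only clearly prespecified response to the same value is referral, and any dosing action is left to judgement. This covers half of main-period doses and up to 72% of all planned doses, the latter assuming full extension uptake. It should be fixed because it concerns the identified toxicity at the smallest margin and the remedy is cheap. The conclusion is limited to prespecified against discretionary action. If the sponsor intends the clause as a standing rule, the text still needs to say so and to be aligned with section 7.10.

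**What to change.** Amend Protocol Table 2, Protocol 7.10 and SAP 2.2.1 to name 40 mg/kg and to state:
- R2* above 369 Hz in any subject, at any scheduled or unscheduled liver MRI and any dose level, holds further dosing, at minimum for that subject, pending SMC review and in addition to hepatology referral.
- Each liver MRI is read before the next dose is given.
- The rule acts at Visit 6 for all of Cohorts 2 and 3, at Cohort 1 Visit 11 (before the first 40 mg/kg dose) and Visit 14, and as an extension entry check at Cohort 1 Visit 20 and Cohorts 2 and 3 Visit 12.

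Table 2's existing stop at the two Day 85 reviews stays as it is.

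This uses scans already scheduled. The cost is some extra SMC review and possible dose delays while a scan is read or discussed.

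Two additions are worth considering but are not needed for the hold to work. One is to apply the 139 Hz escalation limit to Cohort 2's step up to 40 mg/kg, since a hold above 369 Hz leaves values between the two limits unaddressed. The other is a mid-extension liver MRI, which would be a new procedure.
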